4.3. Analysis Sets

The following analysis populations are defined for this study.

4.3.1. Screen Failure Population

The Screen Failure (SF) Population is defined as the set of patients who consent to participate in the study but who are not subsequently randomly assigned to treatment. Individuals who do not meet the criteria for participation in this study (screen failures) may be rescreened once. Patients who failed Screening once but were subsequently rescreened and randomized will not be included in the SF Population. A patient is considered enrolled once the patient has been randomized to study treatment.

4.3.2. Intent-to-Treat Population

The Intent-to-Treat (ITT) Population consists of all patients who are randomized to study treatment, regardless of whether they actually received study treatment. The ITT Population will be the primary analysis population used for the efficacy analyses. The ITT Population will be analyzed according to treatment as randomized.

4.3.3. Per Protocol Population

The Per-Protocol (PP) Population consists of all patients included in the ITT Population who have no study deviations that may substantially affect the efficacy results. Examples of study deviations that lead to PP exclusion include receiving a different study treatment than randomized or concomitant use of prohibited medication that would substantially affect the efficacy results. The final determination on study deviations, and thereby the composition of the PP Population, will be made in blinded fashion prior to the unblinding of the database and will be documented separately. The PP Population will be used in efficacy analyses to support the primary efficacy analyses based on the ITT Population. The PP Population will be analyzed according to actual treatment received.

Additional details regarding the collection of study deviations and designation as significant/non-significant are presented in Section 5.2.

4.3.4. Safety Population

The Safety Population includes all randomized patients who receive at least 1 dose of zetomipzomib or placebo. The Safety Population will be the population used for the safety analyses. The Safety Population will be analyzed by treatment group as actually received.

5. SUBJECT DISPOSITION

5.1. Disposition

Screen failures and reason for screen failure will be summarized and listed for the Screen Failure Population. For patients who failed Screening twice, only the most recent reason(s) for screen failure will be summarized. All screen failure data will be included in the data listing, with rescreening status clearly indicated.

The number and percentage of patients in each of the following categories will be summarized by treatment group and overall, separately for both the ITT and Safety Populations:

- Inclusion in each analysis population (ITT, PP, Safety)
- Ongoing on study treatment
- Completed study treatment
- Discontinued study treatment
 - Reason for discontinuation
- Ongoing on study
- Completed study
 - Week 37
 - Week 53
 - Week 56 (Safety follow-up; EOS)
- Terminated early from study
 - Reason for early termination

Patient disposition will be listed for the ITT Population.

In addition, the number and percentage of patients by region, country and investigational site will be summarized by treatment group and overall for the ITT Population. Regions/countries are as follows; the first digit of the corresponding site numbers in the electronic data capture system (EDC) are indicated in brackets:

- Europe, Middle East, and Africa (EMEA) ["1"]: Croatia, Greece, Portugal, Serbia, South Africa, Spain, United Kingdom
- Asia Pacific ["2"]: Australia, China, India, Republic of Korea, Malaysia, Philippines, Singapore, Taiwan (Province of China)
- North America ["3"]: United States
- Latin America ["4"]: Argentina, Brazil, Colombia, Guatemala, Peru

5.2. Study Deviations

All potential study deviations will be identified by the study team and indicated as either significant or non-significant in the Study Deviation Rules Document (SDRD). The severity of

Statistical Analysis Plan, Version 1.0 Date Issued: 24Jul2024

each study deviation (ie, its impact on excluding the patient from one or more analysis populations) as initially assessed by the statistical team will also be indicated in the SDRD. Significant deviations are defined as important study deviations that affect the primary efficacy and/or safety assessments, the safety or mental integrity of a patient, or the scientific value of the study. Non-significant deviations are defined as study deviations that are identified but do not significantly impact the endpoints, safety or mental integrity of a patient, or the scientific value of the trial.

The significance and severity of each study deviation will be reviewed by the cross-functional study team on a regular basis during the course of the study; the SDRD is a living document and may be updated based on the findings of the ongoing team review. However, all severe study deviations leading to exclusion from the PP or other analysis populations must be reviewed and confirmed in a blinded manner at a Blinded Data Review Meeting held prior to the IA, primary analysis at Week 37, and final analysis/database lock at end of study.

The number and percentage of patients with at least one significant study deviation will be summarized by treatment group and overall for the ITT Population. Significant study deviations will be further summarized by deviation type (Protocol Deviation or ICH/GCP Deviation) and subtype.

All study deviations will be listed for the ITT Population, with significant and non-significant deviations clearly identified.

6. DEMOGRAPHICS AND BASELINE CHARACTERISTICS

Demographic information and baseline characteristics will be summarized by treatment group and overall for the ITT Population. They will also be listed for the ITT Population.

6.1. Demographics

The following demographic information will be presented:

- Age (years)
- Age group (≤ 30 years,>30 years)
- Sex at birth as integrated from RTSM (Male, Female)
- Is the patient of childbearing potential?
 - If Female at birth (Yes, No)
 - If No, summarize reason (Menopause ≥2 years, Hysterectomy, Bilateral oophorectomy, Non-therapy-induced amenorrhea ≥12 months, Bilateral salpingectomy)
 - If Male at birth (Not applicable)
- Ethnicity (Hispanic or Latino, Not Hispanic or Latino, Not Permitted)
- Race (White, Black or African American, Asian, American Indian or Alaska Native, Native Hawaiian or Other Pacific Islander, Not Permitted, Other)
- Baseline weight (kg)
- Baseline height (cm)
- Baseline body mass index (BMI) (kg/m²)

6.2. Baseline Disease Characteristics

The following baseline disease characteristics from the "Medical History – Systemic Lupus Erythematosus" eCRF page will be summarized by treatment group and overall for the ITT Population and the Safety Population.

- Time from SLE diagnosis to Screening (years)
 - Calculated as [(Screening date SLE diagnosis date)/365.25]
 - Partial SLE diagnosis date will be imputed as specified in Section 4
- Time from LN diagnosis to Screening (years)
 - Calculated as [(Screening date LN diagnosis date)/365.25]
 - Partial LN diagnosis date will be imputed as specified in Section 4
- Time from renal biopsy used for study inclusion to Screening (months)
 - If biopsy performed prior to Screening visit, calculate as [(Screening date renal biopsy date)/30.44]
 - If biopsy performed during Screening period, set to 0

- Did patient have protocol-required chest x-ray (Yes, No)
 - If Yes:
 - When was chest x-ray performed (During Screening period, Within 90 days of IC)
 - Results (Normal; Abnormal, not clinically significant [NCS]; Abnormal, clinically significant [CS])
 - Did chest x-ray show evidence suggestive of active tuberculosis (TB) disease (Yes, No)
- LN class as integrated from RTSM (Class III/IV +/- V LN, pure Class V LN) stratification factor
- LN classes: Class III only, Class IV only, Class III + V, Class IV + V, Class V only
- Lesions (Class III/IV)
 - Chronic only {should be screen failure; do not present category on table if n=0}
 - Active only
 - Active and chronic
 - Unknown
- Average 24-hour UPCR as integrated from RTSM ($\leq 3.0, >3.0$) stratification factor
- 24-hour UPCR (mg/mg)
 - See Section 4 for derivation of baseline 24-hour UPCR
- eGFR value (mL/min/1.73 m^2) (<60, \geq 60)
- Treatment naïve (none or ≤3 months) (Yes, No)
- Number of prior LN flares (excluding the current flare)
- Treatment refractory (Yes, No, Not Available)
 - If Yes, summarize the number and percentage of patients with each applicable prior treatment
 - Cyclophosphamide
 - Mycophenolate/MMF
 - Tacrolimus
 - Voclosporin
 - Cyclosporin
 - Rituximab
 - Obinutuzumab
 - Belimumab
 - Anifrolumab
 - Leflunomide

- Bortezomib
- Eculizumab
- IV immunoglobulin
- Other
- IV methylprednisolone planned total dose as integrated from RTSM (0 to <500 mg, 500-1000 mg, or >1000 to 3000 mg) stratification factor

The following additional baseline information will be similarly summarized for the ITT Population:

- Anti-dsDNA antibody (IU/mL)
- Categorical anti-dsDNA antibody
 - Positive (>24 IU/mL)
 - Negative (≤24IU/mL)
- C1q autoantibody (positive > 19 U or negative ≤ 19 U)
- Complement C3 (mg/dL)
- Complement C4 (mg/dL)
- Categorical complement (low C3, low C4, low C3 or low C4)
- Clinical lupus disease assessments
 - SLEDAI-2K Total Score
 - SLEDAI-2K positive for any of the following: Hematuria, Pyuria, or Casts
 - 28-Joint Count (both tenderness and swelling)
 - PGA
- EQ-5D-5L
 - Utility Index
 - EQ-VAS of general health

6.3. Medical History

General medical history will include all prior (ie, started before first dose of study treatment) medical conditions, complications, procedures, and surgeries not related to SLE as captured on the "Medical History" eCRF page. General medical history data will be coded using the Medical Dictionary for Regulatory Activities (MedDRA) Version 26.1 or higher.

The number and percentage of patients with any general medical history will be summarized overall and for each system organ class (SOC) and preferred term (PT) for the Safety and ITT Populations. SOCs will be presented in descending order of frequency overall and PTs and alphabetically in the event of ties. PTs within each SOC will be presented in descending order of frequency overall. At each level of summarization, patients will be counted once if they reported more than one event.

All general medical history data will be listed for the ITT Population.

6.4. Inclusion and Exclusion Criteria

Refer to Sections 4.2 and 4.3 of the study protocol for study inclusion/exclusion criteria.

Inclusion/exclusion criteria violations will be summarized by treatment group, type (inclusion or exclusion), and criterion. Criteria will be presented descending order of patient frequency overall, and criterion number (in case of ties). Only those inclusion/exclusion criteria that were violated by ≥1 patient will be included in the summary.

All inclusion/exclusion criteria violations will be listed for the ITT Population.

6.5. Other Background Information

6.5.1. European Alliance of Associations for Rheumatology/American College of Rheumatology Criteria for SLE

European Alliance of Associations for Rheumatology (EULAR)/American College of Rheumatology (ACR) criteria for SLE (Aringer et al., 2019) will be assessed at Screening. See Appendix 3 for a listing of EULAR/ACR criteria.

EULAR/ACR criteria will be listed for the ITT Population.

6.5.2. Infectious Disease Blood Tests

Screening blood tests for infectious diseases including TB, hepatitis B virus surface antigen (HBsAg), hepatitis B core antibody (HBcAb), hepatitis C antibody, and human immunodeficiency virus (HIV) will be performed at the Screening visit only. Positive screens may require additional testing.

All results, other information related to infectious disease Screening, and country will be listed for the ITT Population.

6.5.3. Serum Pregnancy Test Results

Serum pregnancy test results at Screening will be listed for the ITT Population.

7. TREATMENTS AND MEDICATIONS

7.1. Prior and Concomitant Medications and Procedures

Prior and concomitant medications required by the protocol (ie, IV methylprednisolone, MMF or equivalent, and oral corticosteroids) will be identified directly on the eCRF. All other prior and concomitant medications (including all prescription medications, over-the-counter preparations, vitamins, and supplements) and procedures will be coded according to the World Health Organization drug dictionary WHODrug-Global-B3 Version 202309 or higher. Concomitant medications used in the study will be defined as medications used between the first dose date of investigational medicinal product (IMP) and through last follow-up visit. Prior medications will be defined as medications used and stopped prior to the first dose date of study treatment (ie, medications started before the first dose, not including the medications that continue during the study treatment).

Prior and concomitant medications and procedures will be summarized and listed as described below.

Rescue medications during the treatment period will be summarized and listed as described below.

See Section 4 for imputation of partially missing start/stop dates for prior and concomitant medications.

7.1.1. Protocol-Required Background Medications

7.1.1.1. IV Methylprednisolone

Patients will receive IV methylprednisolone (total dose of 1 g for those weighing >45 kg and 500 mg for those weighing ≤45 kg) on Day 1 (+/- 7 days) unless a patient had IV methylprednisolone within 3 months prior to Screening or at the Investigator's discretion when a patient has had an inadequate response or adverse effects from prior administration. A total dose of IV methylprednisolone up to 3000 mg may be permitted.

Rescue use of IV methylprednisolone is collected directly on the eCRF. Any rescue use of IV methylprednisolone after the first dose of study treatment on Day 1 is considered a treatment failure. Treatment failures will be independently adjudicated by the CEC, in accordance with procedures documented in the CEC Charter.

All prior IV methylprednisolone use and concomitant use through the end of study will be collected on the "Prior and Concomitant IV Methylprednisolone" eCRF form. IV methylprednisolone use will be summarized separately for the following categories in both the ITT and Safety Populations:

- IV methylprednisolone use within 90 days prior to Screening
- IV methylprednisolone from IC date to Day 8
- Concomitant dosing of IV methylprednisolone as rescue therapy (Day 9 through EOS)
- Concomitant dosing of IV methylprednisolone not as rescue (Day 9 through EOS)

7.1.1.1. Prior to first dose of study treatment

The number and percentage of patients with any prior use of IV methylprednisolone and indication for use (eg, LN, SLE besides LN, Other) will be summarized by treatment group. Patients may be included in more than one indication category.

7.1.1.1.2. Day 1 (+/- 7 days)

- The following will be summarized by treatment group for Day 1 dosing: Number and percentage of patients in each IV methylprednisolone dosing category:
 - Planned total dose, as integrated from RTSM (0 to <500 mg, 500-1000 mg, or >1000 to 3000 mg) stratification factor
 - Actual total dose received
 - 0, >0 to <500 mg, 500-1000 mg, >1000 to 3000 mg, >3000 mg
- Total dose received (mg), if >0
 - Overall
 - In patients weighing <45 kg
 - In patients weighing ≥45 kg

Protocol-required IV methylprednisolone dosing on Day 1 may actually occur on Day 1 (+/- 7 days). Protocol-required dosing can be identified by $-7 \le$ dosing start day \le 8, indication = Lupus Nephritis, and rescue medication = No.

7.1.1.1.3. IC to Day 15

IV methylprednisolone dosing will also be summarized similarly for the time Period ranging from IC date to Day 15 of study.

- Total dose received (mg), if >0
 - Overall
 - In patients weighing <45 kg
 - In patients weighing ≥45 kg

7.1.1.4. Concomitant dosing as rescue therapy

The number and percentage of patients receiving concomitant IV methylprednisolone as rescue therapy and total dose received (mg) will be summarized by treatment group.

7.1.1.5. Concomitant dosing not as rescue therapy

The number and percentage of patients receiving concomitant IV methylprednisolone not as rescue therapy and total dose received (mg) will be summarized by treatment group.

All IV methylprednisolone use will also be presented in a single listing for the ITT Population, with prior use, protocol-required dosing on Day 1 (+/-7 days), dosing from IC date to Day 15, indication (LN, SLE besides LN, AE, Other), and any rescue therapy clearly identified.

7.1.1.2. Mycophenolate Mofetil (MMF)

All patients will receive daily MMF or equivalent ("MMF") for 52 weeks at a target dose of 2 g/day, in keeping with the standard of care. Doses from 1 g/day to 3 g/day are permitted with consultation of the Medical Monitor.

Patients already receiving MMF at Screening will continue their current dose or, if receiving >2 g/day, will decrease the dose to 2 g/day on Day 1 (Week 1) unless a higher dose (up to 3 g/day) is approved by the Medical Monitor. If >2 g/day is permitted, this dose will not be continued for more than 24 weeks in total nor after Week 25.

Patients who are not receiving MMF at Screening will start MMF during the first week (after Week 1 dose of zetomipzomib or placebo) at 1 g/day and increase to 2 g/day during the second week (after Week 2 dose of zetomipzomib or placebo).

Changes to the patient's MMF dosing regimen are not permitted after Week 25, unless for tolerability issues (Protocol, Section 6.2.1.3). MMF or equivalent dose >2 g/day after Week 25 is considered a treatment failure. Treatment failures will also be independently adjudicated by the CEC, in accordance with procedures documented in the CEC Charter.

All prior MMF use and concomitant use through the end of study will be collected on the "Prior and Concomitant MMF or Equivalent Medications" eCRF form. MMF use will be summarized separately for prior and protocol-required concomitant dosing for both the ITT and Safety Populations.

Prior Use

The number and percentage of patients with any prior MMF use and type of medication used (MMF, MPA, MPS, Other) will be summarized by treatment group. Patients may be included in more than one medication type category.

Concomitant Use (protocol-required dosing)

The following will be summarized by treatment group:

- Number and percentage of patients currently receiving MMF at Screening* (Yes, No)
 - If Yes: Total daily dose at Screening (g/day)
- Average total daily dose (g/day) by study week (Day 1/Week 1 and Week 2 through Week 53)
- Number and percentage of patients with any total daily dose >2 g/day after Week 25 (study day 169)
- Number and percentage of patients with any total daily dose < 1g/day after Week 3 (study day 15)

*Use of MMF at Screening is defined as any use of MMF or equivalent within the 14-day period prior to Screening date.

As needed, total daily dose as recorded on the eCRF will be converted to MMF equivalent in g/day directly within the EDC system. This derived value will be used for all MMF analyses. Details regarding the derivation are in Appendix 2.

A patient's MMF regimen may be daily, may vary by day(s) of the week (eg, higher dosage Monday-Friday and lower dosage Saturday-Sunday), or have another schedule (eg, every other day) during the course of the study. The eCRF will record the start/stop date and total daily dose associated with each unique regimen for each patient. The total daily dose for each day within the start/stop date interval, inclusive, will be determined based on the regimen. Days within a recorded start/stop date interval with no available dosing information will be assigned a dose of 0.

Total daily dose (g/day) on Day 1 (Week 1) will be summarized separately. For all other study weeks ≥ 2 , average total daily dose (g/day) for Week X will be calculated as {[sum of total daily dose (g/day) over the 7-day period prior to Week X]/7}. The start and stop day (inclusive) of the 7-day period prior to Week X is defined below.

```
Start day of Week X: Day [(X-1)*7-5]
Stop day of Week X: Day [(X-1)*7+1]
```

Average total daily dose (g/day) will only be computed for Week X if there is an available dose value ≥ 0 for every day in the Week X calculation (ie, for all 7 days).

Average total daily dose (g/day) by week will be presented graphically by treatment group for the ITT Population.

• Average total daily dose of MMF from Day 1 through Week 53 (for patients who completed study treatment) and from Day 1 through EOT (for patients who terminated treatment early) will also be summarized by treatment group for the ITT Population.

All MMF or equivalent use will be listed for the ITT Population, with all prior use, protocol-required concomitant use, any concomitant doses <1 g/day or >3 g/day or any doses >2 g/day after Week 25 clearly identified.

7.1.1.3. Corticosteroids

All patients will receive daily oral corticosteroids (0.3 to 0.5 mg/kg/day, maximum of 40 mg/day) for 52 weeks.

For patients already receiving prednisone or equivalent ("prednisone") at a dose of 40 mg/day or higher at Screening, the dose will be tapered to ≤40 mg/day by Day 1 (Week 1). All patients will initiate prednisone tapering starting on Day 15 (Week 3) and should reduce the dose to ≤5 mg/day by Week 17. See the recommended tapering schedule in Table 2 of the study protocol.

Patients who exceed a dose greater than 10 mg/day prednisone for ≥ 3 consecutive days or for ≥ 7 days in total during the 8 weeks prior to the renal response assessment at Week 37 (ie, primary endpoint) will be considered a treatment failure.

All use of corticosteroids including topical use will be collected from at least 24 weeks prior to Screening and through the end of study on the "Prior and Concomitant Corticosteroid"

Medications" eCRF form. Corticosteroid use will be summarized separately for prior use, protocol-required concomitant dosing, and other concomitant use for both the ITT and Safety Populations.

Prior Use

The number and percentage of patients will be summarized by treatment group for the following:

- Any prior use of corticosteroids (Yes, No)
 - If Yes:
 - Type of medication used (Betamethasone, Cortisone acetate, Dexamethasone, Hydrocortisone, Methylprednisolone, Prednisolone, Prednisone); patients may be included in more than medication type category
 - Indication for use (eg, LN, SLE besides LN, Other)

Patients may be included in more than one medication type and/or indication category.

Concomitant Use

The following will be summarized by treatment group:

- Number and percentage of patients receiving oral corticosteroids at Screening*
 (Yes, No)
 - If Yes: Total daily dose at Screening (mg/day)
- Average total daily dose (mg/day):
 - By study week (Day 1/Week 1 and Week 2 through Week 53)
 - By study week category (Weeks 1-2, Weeks 3-4, Weeks 5-6, Weeks 7-8, Weeks 9-12, Weeks 13-16, Week 17-20, Weeks 21-24, Weeks 25-28, etc.)
- Number and percentage of patients with >10 mg/day for ≥3 consecutive days or for ≥7 days in total during the 8 weeks prior to the renal response assessment at Week 37 (ie, primary endpoint)
- Number and percentage of patients with ≤ 10 mg/day for 8 weeks prior to the renal response assessment (eg. at Week 37 for the primary endpoint)
- Number and percentage of patients at Week 17 with ≤ 5 mg/day
- Number and percentage of patients at Week 17 with 0 mg/day
- Number and percentage of patients at Week 25 with $\leq 10 \text{ mg/day}$
- Average total daily dose of oral corticosteroids from Day 1 through Week 53 (for patients who completed study treatment)
- Average total daily dose of oral corticosteroids Day 1 through EOT (for patients who terminated treatment early)

^{*}Use of oral corticosteroids at Screening is defined as any use of oral corticosteroids within the 14-day period prior to Screening date.

As needed, total daily dose as recorded on the eCRF will be converted to prednisone equivalent in mg/day directly within the EDC system. This derived value will be used for all analyses of involving protocol-required oral corticosteroids. Details regarding the derivation are in Appendix 2.

A patient's oral corticosteroids regimen may be daily, may vary by day(s) of the week (eg, higher dosage Monday-Friday and lower dosage Saturday-Sunday), or have another schedule (eg, every other day) during the course of the study. The eCRF will record the start/stop date and total daily dose associated with each unique regimen for each patient. The total daily dose for each day within the start/stop date interval, inclusive, will be determined based on the regimen. Days within a recorded start/stop date interval with no available dosing information will be assigned a dose of 0.

Total daily dose (mg/day) on Day 1 (Week 1) will be summarized separately. For all other study weeks ≥ 2 , average total daily dose (mg/day) for Week X will be calculated as {[sum of total daily dose (mg/day) over the 7-day period prior to Week X]/7}. The start and stop day (inclusive) of the 7-day period prior to Week X is defined below.

```
Start day of Week X: Day [(X-1)*7-5]
Stop day of Week X: Day [(X-1)*7+1]
```

Average total daily dose (g/day) will only be computed for Week X if there is an available dose value ≥ 0 for every day in the Week X calculation (ie, for all 7 days).

Average total daily dose (mg/day) by week will be presented graphically by treatment group for the ITT Population.

Other Concomitant Use (not protocol-required)

All other concomitant oral, intravenous, intramuscular, or intra-articular corticosteroid use not required by the study protocol will be summarized in a similar manner as prior use.

All corticosteroids use will be presented in a single listing for the ITT Population, with all prior use and protocol-required concomitant use clearly identified.

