3.2.1.4. Treatment Failure

A patient experiencing one or more of the following criteria define treatment failure:

- Prednisone or equivalent* beyond that permitted (see Section 6.2.1.2 of the study protocol), to include:
 - >10 mg/day for ≥3 consecutive days or for ≥7 days in total during the 8 weeks prior to the renal assessment at
- MMF or equivalent* >2 g/day after Week 25
- Requiring rescue therapy (see Section 6.2.3 of the study protocol for details), as verified by the CEC

Statistical Analysis Plan, Version 1.0 Date Issued: 24Jul2024

• Use of prohibited medications (see Section 6.2.4 and Appendix 2 of the study protocol for details) or inappropriate use of the required concomitant medications (see Section 2.2.5 of the study protocol), as determined through manual data review by the CEC

• Discontinuation of zetomipzomib or placebo

Whenever possible, a complete disease activity assessment (eg, SLEDAI-2K, SLE flare index, PGA) and laboratory assessments (hematology, chemistry, urinalysis, anti-dsDNA, and C3 and C4) should be performed to document flare prior to initiating treatment that results in a treatment failure designation. Treatment failure does not necessarily require discontinuation of zetomipzomib or placebo. See Section 8.1.2 of the study protocol for individual patient stopping rules.

Treatment failure will be adjudicated in blinded fashion by the CEC. Details of this process will be provided in the separate CEC Charter.

*See Appendix 2 for dose conversion of other corticosteroid medications to prednisone equivalent and conversion of mycophenolic acid (MPA) and mycophenolate sodium (MPS) to MMF equivalent.

3.2.1.5. **Relapse**

Relapse is defined as loss of CRR at 2 consecutive time points

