8.2. Primary Efficacy Endpoint

The primary efficacy endpoint is the proportion of patients who achieve CRR at Week 37. See Section 3.2.1 for details. CRR at Week 37 will be adjudicated by the CEC, in accordance with procedures documented in the CEC Charter. Both the adjudicated and original (non-adjudicated, as programmed) primary endpoint information will be retained on the analysis database, but the adjudicated endpoint will be used for the primary analysis.

To be a responder, a patient must complete the Week 37 visit and not be considered a treatment failure as defined in Section 3.2.1.

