8.4.3. Analysis of Binary Secondary Efficacy Endpoints

Binary secondary efficacy endpoints include:

- Proportion of patients achieving CRR (at Weeks 25, 37, and 53) with successful taper of prednisone or equivalent to ≤5 mg by Week 17
- Proportion of patients achieving CRR (at Weeks 25, 37, and 53) with no use of prednisone or equivalent during the 8 weeks prior to the renal response assessment
- Proportion of patients with UPCR ≤0.5 at Weeks 13, 25, 37, and 53
- Proportion of patients achieving CRR with UPCR ≤ upper limit of normal (ULN) at Weeks 25, 37, and 53

Binary secondary efficacy endpoints will be analyzed using similar CMH methods as the main analysis of the primary estimand.

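### Unknown steroid or MMF doses inside a recorded interval are set to 0, which favours the Week 17 taper endpoint and the programmed >10 mg/day count

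*SAP*

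**What the plan says.** SAP 7.1.1.3 describes how daily steroid doses are built. The eCRF holds start and stop dates and a total daily dose for each regimen. A regimen may be daily, may vary by weekday, "or have another schedule (eg, every other day) during the course of the study". Each day's dose inside the interval is taken from the regimen. Then comes the rule at issue: "Days within a recorded start/stop date interval with no available dosing information will be assigned a dose of 0". SAP 7.1.1.2 repeats it word for word for MMF.

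A weekly average is computed only if a dose value of 0 or more is available "for every day in the Week X calculation (ie, for all 7 days").

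Three kinds of result use daily steroid doses:

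- **Taper endpoint.** SAP 8.4.3 lists CRR at Weeks 25, 37 and 53 with a taper to ≤5 mg by Week 17. SAP 7.1.1.3 also counts patients at ≤5 mg/day and at 0 mg/day at Week 17.
- **Steroid-free endpoint.** SAP 8.4.3 lists CRR "with no use of prednisone or equivalent during the 8 weeks prior to the renal response assessment". Section 8.5.3 has PRR versions of both endpoints.
- **The >10 mg/day criterion.** SAP 3.2.1.4 gives it as ">10 mg/day for ≥3 consecutive days or for ≥7 days in total during the 8 weeks prior to the renal assessment at" a response visit, and SAP 7.1.1.3 tabulates it for Week 37.

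On who decides failure, SAP 3.2.1.4 says "Treatment failure will be adjudicated in blinded fashion by the CEC", and SAP 8.2 says "the adjudicated endpoint will be used for the primary analysis".

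**The concern.** Zero is not a neutral fill-in value for these endpoints. It is the lowest possible steroid dose, so a day on which nobody knows what the patient took is scored as a day without steroid. The plan treats other missing response information differently: SAP 8.2.2 counts a missing Week 37 CRR as non-response, and Protocol 2.2.1 requires a responder to have data available.

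The SAP gives no other day-level derivation for the taper and steroid-free endpoints. Section 4 says that no imputation beyond what the SAP lists is planned, and no sensitivity analysis addresses missing doses. Steroid-sparing is part of the trial's stated rationale (Protocol 1.3), so a reader will give weight to these endpoints. At stake are apparent tapers that did not happen and short courses above 10 mg/day that drop out of the programmed count.

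**Working it through.** No sample size, power or alpha figure rests on this rule, so there is no stated figure to reproduce. The check applies the SAP's own day-level rules with gaps set to 0.

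**1. What the sentence covers.** Because each day's dose already follows from the regimen, an off-day of an alternate-day schedule has dosing information, namely zero. Read literally, the extra sentence applies to whatever is left: days inside an interval for which the regimen yields no dose. It therefore reaches unknown doses.

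**2. The completeness check.** It asks for a value ≥0 on all 7 days. A filled-in 0 passes. Inside an interval the count of days with a value is always 7, so the check cannot fail there. It still works for days outside every interval, which this rule does not fill.

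**3. Taper at Week 17.** The window begins at "Start day of Week X: Day [(X-1)*7-5"]. With X = 17 this is 16 × 7 − 5 = Day 107; the stop day is 16 × 7 + 1 = Day 113. For a constant true dose d with m gaps, the derived mean is d × (7 − m)/7.

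| True dose (mg/day) | Fewest gaps giving a mean ≤5 mg | Derived mean (mg/day) |
|---|---|---|
| 7.5 | 3 | 7.5 × 4/7 = 4.29 |
| 10 | 4 | 10 × 3/7 = 4.29 |
| 15 | 5 | 15 × 2/7 = 4.29 |
| 20 | 6 | 20 × 1/7 = 2.86 |

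SAP 8.4.3 does not say whether the taper is judged on this mean or on a single day. On a single day, one gap is enough at any dose.

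**4. The >10 mg/day count.** A flag needs a run of at least 3 days or a total of at least 7 days above 10 mg within 56 days. The assumed case is one isolated course at 15 mg/day on a 5 mg/day background, trying every placement of the gaps.

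| Course length (days) | Fewest gaps that remove the flag |
|---|---|
| 3 to 5 | 1 |
| 6 to 8 | 2 |
| 9 | 3 |
| 10 | 4 |
| 14 | 8 |
| 56 | 56 − 6 = 50 |

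For example, an 8-day course with days 3 and 6 zeroed leaves runs of 2, 2 and 2 days and a total of 6, so neither limb is met. True off-days do no such harm: alternate-day 20 mg gives 28 days above 10 mg in 56 and is still flagged.

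**5. Steroid-free for 8 weeks.** All 56 days must be zero, a gap inside an interval, or outside every interval. One recorded non-zero day defeats it.

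**6. MMF.** SAP 7.1.1.2 counts patients with any daily dose below 1 g after Week 3, so one filled-in zero is enough to add a patient. It also counts any daily dose above 2 g after Week 25, and a zero can hide such a day. The two errors do not point the same way.

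**The case against.** The strongest defence is that the sentence was written for off-days. It follows directly on the weekday and every-other-day examples, and a regimen with dates and a dose fills its own days. An unknown day then needs a record with dates but no usable dose, which should be uncommon because missing data are queried (Protocol 11.11) and background-medication compliance is monitored (Protocol 6.2.1). This is a fair account of the likely intent, and it suggests that gaps may be few. It does not change what the text instructs a programmer to do.

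Three stronger readings are tempting, and the documents do not support them.

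- A reader might infer that a wholly missing steroid record counts as steroid-free. The rule applies only inside a recorded interval. A patient with no record is not zero-filled, and how such a patient is classified on the taper and steroid-free endpoints is not stated.
- A reader might infer that the rule hides treatment failures in the primary analysis. That analysis uses blinded CEC adjudication. Whether the CEC sees raw or zero-filled doses is left to a charter that is not among these documents. What is clearly exposed is the programmed count.
- A reader might infer that any gap makes a steroid-free responder. Step 5 shows otherwise, and a recorded prednisone interval overlapping the window is itself some evidence of use.

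It is also true that the taper and steroid-free CRR endpoints are other secondary endpoints, with nominal p-values and no multiplicity control (SAP 8.1). This limits the consequences.

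**Conclusion.** The point holds in a limited form. As written, the SAP turns an unknown dose inside a recorded interval into the value most favourable to the steroid endpoints, and its own completeness check cannot detect this. The Week 17 taper endpoint is the most exposed, followed by short courses in the programmed >10 mg/day count. Long courses and the steroid-free endpoint are hard to distort. For MMF the direction is mixed.

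The mechanism can be shown exactly, but the size of the bias cannot be computed, because no document gives the frequency of gaps. A reader might multiply an assumed gap rate by the design CRR rates. With 2 to 10% of responders wrongly credited, that gives 0.40 × (0.02 to 0.10) = 0.8 to 4.0 points in an arm at 40% and 0.20 × (0.02 to 0.10) = 0.4 to 2.0 points in an arm at 20%, so up to 2 points of false difference. This shows only that equal gap rates need not cancel. The 2 to 10% is an assumption, and the product treats every gap as a misclassification, which steps 3 to 5 contradict. It should not be quoted as an estimate.

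This should be corrected before unblinding. On these documents it is not a demonstrated threat to the primary result.

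**What to change.** - In SAP 7.1.1.2 and 7.1.1.3, assign 0 only to days that the recorded regimen defines as no-dose days. Leave all other days without dosing information missing, so that the 7-day check works again for both drugs.
- For the taper and steroid-free endpoints, count a patient with unresolved missing days in the relevant window as not meeting the criterion. Add a sensitivity analysis that carries the last recorded dose across the gap.
- State how days outside every recorded interval are read. A documented stop of steroid is information rather than a gap; otherwise patients who truly stopped would be scored as unresolved.
- State whether the Week 17 taper is judged on the weekly mean or on a single day.
- State that the CEC reviews raw dosing records with gaps flagged.

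The cost is a few sentences and a small programming change. The downside is slightly lower taper and steroid-free response rates. Counting unresolved gaps as failure is not the only defensible choice, but it matches the non-responder approach the SAP already takes.
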